### Study participants

Adults will be eligible to join the study if they are aged  $\geq 50$  years, living in the community, with MCI defined by the following criteria: i) presence of significant cognitive complaints, defined as  $\geq 3$  complaints on the Memory Inventory for Chinese;[44] ii) abnormal objective cognitive performance defined as  $< -1.5$  standard deviations from age- and education-matched normal persons on the Montreal Cognitive Assessment Hong Kong version (HK-MoCA);[45] and iii) independence in daily living as evaluated through the clinical interview. Participants are required to have poor sleep quality that can be assessed by the Pittsburgh Sleep Quality Index (PSQI).[46] The PSQI consists of 19 items evaluating seven domains of subjective sleep quality in the preceding month. Each subscale is weighted equally on a 0 to 3 scale. A global score is obtained by summing the scores of the subscales, with a higher score indicating worse sleep quality. MCI persons with a global PSQI score of  $> 5$  will be eligible for inclusion. Persons with confirmed dementia,

with known psychiatric conditions, impaired communication, sleep disorders with an organic cause (e.g., sleep apnea, or restless legs syndrome) or due to a medical problem (e.g., pain) and those using hypnotics and other medications known to affect sleep (e.g., steroids, anxiolytics) will be excluded. A total of 60 participants (i.e., 30/study arm) will be recruited for this pilot RCT. The findings of this pilot will provide information for estimating the effect size, which will inform the sample size for a subsequent full-scale RCT.

Intervention group: Empowerment-based CBT-I for MCI

Participants in the intervention group will participate in a 12-week empowerment-based CBT-I comprising face-to-face sessions supplemented with telephone follow-ups. In total, six face-to-face sessions (90 minutes/session) will be conducted in a small group format with 6–8 participants in a group and two 30-minute individual sessions will be scheduled over eight weeks, with the individual sessions arranged in the 4th and 7th week, and this is then followed by two bi-weekly telephone follow-ups. The face-to-face delivery modality is adopted to meet the challenges of mildly impaired cognition faced by MCI persons, whereas the small group format was chosen in accordance with the literature suggesting it has efficacy comparable with the individual format.[50] The group format is more cost-effective, and it can facilitate peer modeling and learning. The face-to-face sessions will cover the following core areas in CBT-I: i) sleep education, ii) sleep hygiene and relaxation, iii) sleep restriction, iv) stimulus control and v) cognitive therapy. The first five sessions will cover these core areas, and a booster session will then follow to summarize the key components of CBT-I and equip the participants with relapse-prevention strategies when sleeping problems recur (Table 1). The content of the CBT-I components complies with the recommendations for managing chronic insomnia by major international sleep associations.[11, 51]

A five-step empowerment approach (Figure 2) will be adopted to implement each face-to-face session to facilitate goal attainment and behavioral maintenance. At the beginning of each session, RA1 will encourage the participants to discuss their usual practice or beliefs about sleep or insomnia related to the core area of that week. The RA1 will make use of various therapeutic communication and counseling skills during the process, which are outlined in Figure 2. Moreover, supportive, non-judgmental and empathetic attitudes will be used to build a rapport with the participants. The RA1 will then deliver a structured educational session about the topic area. The rationales and explicit methods of how to carry out the suggested behaviors will be stated. The content will emphasize assisting participants to understand the linkage between their usual practice (behaviors/thoughts) and the consequences to sleep disruption. The RA1 will then facilitate the participants to identify the discrepancies between their usual practice/dysfunctional beliefs and the recommended best practice for sleep improvement/beliefs that favor better sleep. Easy-to-understand comic stories will be incorporated to illustrate the more abstract concepts about dysfunctional beliefs related to insomnia (for the session on cognitive therapy) and bed-sleep association (for the session on stimulus control). The RA1 will also highlight the possible consequences of these discrepancies on brain health. The RA1 will then assist participants to set self-directed goals related to these areas. During this process, the RA1 will work collaboratively with the participants and ensure that the goals are achievable yet challenging. The RA1 will also work with the participants to develop an action plan for achieving the goals set during each session. After action-planning, a subsequent interactive skill-building session will ensure that participants acquire the skills required to perform specific behaviors. A scenario-based approach will be adopted to train the participants on how to maintain the recommended behaviors. The RA1 will make use of group dynamics by encouraging the discussion among the peers of successful actions, feelings, concerns and perceived barriers to goal achievement. Various memory compensatory strategies will be used to reinforce the educational content, such as memory aids (e.g., memory notebooks, calendars and to-do lists) and mnemonic strategies. Each subsequent session will begin with a discussion of progress in goal attainment and challenges and barriers encountered while implementing the action plan set during the preceding week. The RA1 will also review the key messages delivered in previous sessions.

The RA1 will provide continuous support through telephone calls (two bi-weekly calls) upon the completion of all face-to-face sessions. A telephone record containing the participants' demographic and clinical profile, endorsed dysfunctional beliefs and attitudes about sleep, self-directed goals and action plans will be created to facilitate the telephone support. The RA1 will monitor participants' adherence to the recommended behaviors and goal attainment progress, identify barriers in real-life settings and provide methods of resolving them. The advice and counseling given will be documented to guide subsequent telephone calls.

Control group: Usual care

The control group will receive the standard care provided by the elder community centers. The participants in the control group are required to consent not to participate in any structured cognitive training activities provided by the centers during the study period.

#### Fidelity monitoring of the study intervention

A step-by-step standard manual with sample dialogue will be developed to guide the RA1 in delivering the intervention. Moreover, the PI will randomly select two groups in the intervention arm for fidelity monitoring and checking. The face-to-face sessions will be videotaped, and the telephone calls will be audiotaped after obtaining the participants' consent. A performance checklist will be developed and used for fidelity checking. Two postdoctoral fellows will be invited to review the videos and complete the checklist. In addition, the attendance of the participants will be recorded. All of these data will be used to interpret the study findings.

### **Outcome measures**

Sleep assessment. Three measures were chosen to evaluate sleep pattern and quality by both subjective and objective means according to the recommendations suggested by the international expert consensus.[52] The 19-item Chinese version of the PSQI will be used to assess subjective sleep quality.[53] It is reliable (Cronbach's alpha = 0.83) and has shown good test-retest reliability and discriminant validity.[53] The Chinese version of the Insomnia Severity Index (ISI-C) (7-item)[54] will be used to assess the perceived insomnia severity, consequences of insomnia and the degree of distress related to insomnia. A five-point Likert scale is used, with higher values indicating higher levels of perceived severity of insomnia, more severe consequences of insomnia and a greater degree of distress associated with insomnia. The ISI-C has good internal consistency (Cronbach's alpha = 0.81), construct and discriminant validity.[54] An Actiwatch, which contains an accelerometer to record the frequency and intensity of body movement, will be used to objectively assess sleep patterns. The parameters of sleep pattern include TST, SL, WASO and the ratio of TST to SE. Participants will be instructed to wear the Actiwatch on their non-dominant wrist during sleep for a consecutive seven-day period.

Cognitive assessments. To detect subtle cognitive changes, a battery of cognitive assessments will be used to evaluate various domains of cognition, including the Cantonese version of the Alzheimer's Disease Assessment Scale—Cognitive subscale (ADAS-Cog)[55] for global cognition, the digit span-forward and backward test for attention and working memory, the Hong Kong List Learning Test for episodic memory, and the Color Trails Test for complex attention, executive function and task switching.

HRQoL. The Chinese Hong Kong version of the Short Form Health Survey (SF-12) will be used to measure HRQoL.[56] It consists of 12 items to form two summary scores to reflect people's physical and mental well-being, with higher scores indicating better HRQoL. Its psychometric properties are satisfactory with evidence of good reliability, content and construct validity.[56]

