### **Research plan and methodology**

The proposed study will have two aims: i) to determine the feasibility of an empowerment-based CBT-I in MCI persons; and ii) to examine the preliminary effects of the empowerment-based CBT-I on sleep, cognitive outcomes and HRQoL in persons with MCI. Sleep pattern in terms of time to initiate sleep (sleep latency, SL), number and duration of awakenings after sleep onset (WASO), ratio of total sleep time (TST) to the time spent in bed (sleep efficiency, SE) and sleep quality will be the primary outcomes, and cognitive function and HRQoL will be the secondary outcomes.

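### The Outcome measures section lists TST divided by SE, which equals time in bed and is not sleep efficiency, a primary outcome

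*Combined protocol and SAP*

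**What the plan says.** The Research plan and methodology section names the primary outcomes: sleep latency, wakefulness after sleep onset, sleep efficiency and sleep quality. For the last two it reads: "ratio of total sleep time (TST) to the time spent in bed (sleep efficiency, SE) and sleep quality will be the primary outcomes". So SE is TST over time in bed. Cognitive function and HRQoL are the secondary outcomes.

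The Outcome measures section, under Sleep assessment, turns these into measurements. It opens: "Three measures were chosen to evaluate sleep pattern and quality by both subjective and objective means". The three are the PSQI, the ISI-C and the Actiwatch. On the PSQI it says: "The 19-item Chinese version of the PSQI will be used to assess subjective sleep quality". On the Actiwatch it says: "The parameters of sleep pattern include TST, SL, WASO and the ratio of TST to SE". No sleep measure in this section is labelled primary or secondary. The Data analysis section names no sleep variable, so it does not settle the definition.

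**The concern.** The Actiwatch sentence is what someone programming the outcome data would follow, and its fourth entry is not SE. It divides TST by SE. Because SE already has TST as its numerator, TST cancels and time in bed is left.

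This matters here for two reasons. First, sleep restriction is one of the core intervention components, and the background section on sleep promotion describes it as confining time in bed to the period actually slept. Controls receive usual care. A variable equal to time in bed could therefore differ between arms because participants followed the instruction, without showing that they slept better. Second, the Study participants section says the pilot will supply the effect size for planning a full-scale trial, so a misdefined outcome could be carried into that calculation.

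**Working it through.** There is no stated figure to reproduce; the check is on a definition.

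**Inputs**
- SE = TST / TIB, where TIB is time in bed (Research plan and methodology).
- Listed Actiwatch quantity = TST / SE (Outcome measures, Sleep assessment).
- The TST and TIB values below are assumed for illustration. The protocol gives none.

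**Substitution**

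TST / SE = TST / (TST / TIB) = TIB, for any TST above zero. If SE is held as a percentage, the result is TIB / 100.

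**Numbers**

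| TST (min) | TIB (min) | SE = TST/TIB | TST/SE, SE as proportion | TST/SE, SE as percentage |
|---|---|---|---|---|
| 300 | 480 | 62.5% | 480 | 4.8 |
| 330 | 480 | 68.75% | 480 | 4.8 |
| 330 | 400 | 82.5% | 400 | 4.0 |
| 360 | 450 | 80.0% | 450 | 4.5 |

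- Rows 1 and 2: sleep rises by 30 min in the same time in bed. SE rises by 6.25 percentage points (68.75 − 62.5). The listed quantity does not move.
- Rows 2 and 3: sleep is unchanged and time in bed falls by 80 min. The listed quantity falls by exactly that amount (480 − 400 = 80).

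The listed quantity carries no information about how much of the time in bed is spent asleep.

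**The two sections side by side**

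| Item | Research plan and methodology | Outcome measures |
|---|---|---|
| Sleep latency | primary | listed |
| WASO | primary; number and duration under one label | listed, not defined further |
| SE as TST/TIB | primary | absent; TST/SE in its place |
| Sleep quality | primary | PSQI |
| TST on its own | only as the numerator of SE | listed, no rank |
| ISI-C | not mentioned | listed, no rank |

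The one outright contradiction is the SE row. The last two rows are missing detail.

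**The case against.** The strongest reply is that the primary outcome is defined correctly where primary outcomes are declared. The faulty phrase looks like a clipped version of that definition, and an analyst who knows the field would compute SE properly. This stands in large part: it makes a drafting slip the likely explanation and keeps the severity low. It does not remove the point, because the section that specifies the measurements still contradicts the definition and omits SE.

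Three stronger readings are tempting, and the documents do not support them.

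- *There are two rival sets of primary outcomes.* Outcome measures labels nothing primary, so there is one declared set and one list of measurements. What is open is the rank of TST and ISI-C.
- *The number of awakenings has been dropped.* The declaration reads "number and duration of awakenings after sleep onset (WASO), ratio of total sleep time (TST) to the time spent in bed", with number and duration both under the label WASO, and the Actiwatch list includes WASO. The label is ambiguous in both sections, but nothing is clearly removed.
- *The faulty variable would show a spurious arm difference.* It could, but that requires someone to compute the literal ratio and time in bed still to differ at T1 or T2. The background section describes restriction as temporary, with sleeping time then gradually extended, and T1 follows a 12-week programme. No figure in the protocol shows a lasting difference.

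It is also fair to say that correctly defined SE has time in bed as its denominator, so the correction does not make the outcome independent of sleep restriction. It does restore the numerator, so that more sleep within the same time in bed registers.

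**Conclusion.** Wrong as written, minor severity. Given the protocol's own definition of SE, the fourth Actiwatch parameter is algebraically time in bed. This holds for every participant with non-zero sleep and needs no numerical assumption; the TST and TIB values above only illustrate it. One of the declared primary outcomes is thus mis-stated in the section that specifies its measurement, although its definition elsewhere is right. Any effect on results depends on the phrase being followed literally. Sample size (60, with 30 per arm) and the two-sided 0.05 level are unaffected.

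**What to change.** In Outcome measures, Sleep assessment, replace the faulty ratio with SE = 100 × TST / time in bed, matching Research plan and methodology.

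In the same edit, and before results are seen:
- state whether WASO means the number of awakenings, minutes awake after sleep onset, or both;
- give TST and ISI-C a primary or secondary status. Which rank they receive is the sponsor's choice.

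The SE correction costs one line of text and changes no instrument, visit, sample size or significance level. Settling WASO and the two ranks also needs only wording; what the sponsor gives up is the freedom to decide them later.

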### **Ethical Consideration:**

This study followed the Declaration of Helsinki on medical protocol and ethics. Ethics approval will be obtained from the Institutional Review Board of the University of Hong Kong/Hospital Authority Hong Kong West Cluster. Patients are voluntary participants in the study. A written informed consent, which will include the research title, purpose, explanation of the research, and the procedures of the study, will be obtained from each eligible participant. Risks and benefits are also explained clearly to the participants.

Participants have the right to withdraw from the study at any time. They will be protected from discomfort and harm during the study. Further, anonymity and confidentiality of the participants will be strictly protected. Their decision of participating in the study will not affect the quality of present or future care they receive in the hospital.

